2.0 OBJECTIVES

2.1 Primary objectives:

Assess 5-year biochemical failure free rate (BFFR) associated with the combined hypofractionated dose regimen and ADT. The BFFR is defined as a binary indicator whether

PSA has increased by 2 ng/ml or more above the nadir PSA any time before the end of 5 years.

2.2 Secondary objectives:

- 1) Assess the incidence of grade 3 or greater late GU and GI toxicity and self-reported quality of life data.
- 2) Assess clinical and pathologic control rates associated with the combined hypofractionated dose regimen and ADT using Kaplan-Meier estimates.
- 3) Collect dose/volume and imaging data to allow normal tissue complication probability modeling and targeting assessment for patients treated with hypofractionated radiation therapy.
- 4) Collect whole blood to perform correlative studies for serum cytokine profiling and future biomarker studies.

3.0 PATIENT SELECTION: The target population will be patients with a diagnosis of adenocarcinoma of the prostate who are seen in consultation in the Department of Radiation Oncology (approximately >1000 patients per year).

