6.0 PATIENT ASSESSMENTS

6.1 Study Parameters

- H&P – at initial consult and following treatment protocol
- PSA – At baseline, 3 and 6 months after treatment, then every 6 months until 3 years, and then annually until year 5
- Testosterone – At baseline, 3 and 6 months after treatment, then every 6 months until 3 years, and then annually until year 5
- Bone Scan - at baseline*
- Pelvic CT or other lymph node assessment - at baseline*
- Symptom assessment (IPSS, SHIM, modified EPIC sheet, as per Appendix I) – At baseline, 3 and 6 months after treatment, then every 6 months until 3 years, and then annually until year 5
- Serum ALT, AST and AP at baseline and one month following initiation of ADT.
- Optional Blood draw collected at baseline and at 3 and 24 months following treatment completion. Patients who have initiated ADT prior to consent for optional blood samples will be ineligible to give extra blood samples.
- Seed placement of at least 3 gold seeds at least 1 week prior to first CT simulation if additional image guidance is not being used
- CT simulation will occur prior to radiation treatment as standard of care and then again during radiation any time after fraction 3 as a QA procedure for monitoring prostate rotation in relation to seed placement. However, second CT simulation after fraction 3 is only necessary if patient had fiducial placement.

* CT/MRI and Bone scan optional except for the patients who are:

1. Gleason 4+3
2. >50% cores positive
3. >1 intermediate risk factor (GS 7, PSA ≥ 10 and T2b-T2c).

Safety run-in phase

A phase I trial of SBRT in prostate cancer (n=45) composed of 60% intermediate-risk, localized patients where 22% of men were treated with androgen deprivation has been recently reported (ref. 7). This trial used considerably higher SBRT doses than our current trial (9-10 Gy x5 versus 7.25 Gy x5) and still reported no Grade 3 or 4 GI or GU acute toxicities (<90 days). Therefore, we believe our more modest SBRT fractionation scheme of 7.25 Gy x5 is likely safe in combination with androgen deprivation. To ensure that this combination is safe, the first six patients will be treated and analyzed for toxicity for 3

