8.0 DATA ANALYSIS AND SPECIAL CONSIDERATIONS

8.1 Primary Analysis:

The primary objective is to estimate the 5-year biochemical failure free rate (BFFR) associated with the combined hypofractionated dose regimen and ADT. The BFFR is defined as a binary indicator whether PSA has increased by 2 ng/ml or more above the nadir PSA any time before the end of 5 years. The primary analysis will be performed by first obtaining the Kaplan-Meier (K-M) estimate of the biochemical failure free survival, and then estimating the 5-year biochemical failure free rate (BFFR) from this K-M curve together with 95% confidence interval. Greenwood formula will be used to calculate the variance of K-M estimate.

8.2 Secondary objectives:

8.2.1. Assess the incidence of grade 3 or greater late GU and GI toxicity and self-reported quality of life data.

Kaplan-Meier estimate of the incidence of grade 3 or greater late GU and GI toxicity will be constructed together with 95% confidence interval. Patient reported quality of life will be summarized using means and standard deviation for continuous measures, the contingency tables for categorical measures.

8.2.2 Assess clinical and pathologic control rates associated with the combined hypofractionated dose regimen and ADT.

Assessments will be performed 3 and 6 months after treatment and then every 6 months until 3 years, then annually until year 5. These rates will be estimated from Kaplan-Meier curves together with 95% confidence intervals.

Disease-Free Survival, measured from the date of enrollment to the date of documented progression or date of death using Kaplan-Meier estimates. Progression will be documented by PSA, bone scan, or biopsies.

Time to Local Progression (TLP) will be measured from the date of enrollment to the date of documented local progression using Kaplan-Meier estimates. Patients with new palpable abnormality on digital rectal examination or PSA failure at any point in time will also be offered biopsy to distinguish between local and distant failures. Patients who do not undergo biopsy will be censored at the last point of time they were considered locally controlled by digital rectal examination and PSA and considered not evaluable for further assessment.

Time to Distant Failure (TDF) will be measured from the date of enrollment to the date of documented metastatic disease. Patients who have negative biopsy following PSA failure or palpable abnormality will be considered to have only distant failure.

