8.3 Sample size

The primary endpoint is the 5-year biochemical failure free rate (BFFR) associated with the combined hypofractionated dose regimen and ADT. All patients will be followed for at least 5 years. We expect to observe 5-year BFFR 85% or higher. The annual dropout rate is expected to be at most 1% ~ 2% (or cumulative 5 year dropout rate is less than 10%). If 100 patients will finish 5 year follow up, the width of 95% confidence interval of BFFR will be less than 0.14. To incorporate the dropout rate, the total required sample size will be 110.

8.4 Safety monitoring.

An early stopping boundary will be used to test the hypotheses $H_0: Rt \leq 10\%$ versus $H_1: Rt > 10\%$ where Rt is the rate of grade 3 or greater on either GU or GI toxicity. We derive the one-sided stopping boundary using exact binomial test: at the first stage with 50 patients recruited, if 12 or more patients have experienced grade 3 or greater toxicity with an *attribution* of probably related (see section 10.2), the trial will be stopped. Otherwise, the trial will continue to recruit all 100 patients. If no more than 16 patients out of total 100 patients have experienced grade 3 or greater toxicity as detailed previously, the treatment is considered safe for further investigation. Based on EAST 5 (Copyright © 2009 Cytel Inc) Binomial one-sample exact test for single proportion, this stopping rule gives 87% power to reject unsafe treatment regime if the true toxicity rate is 20%.

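### Section 8.2.1 plans no change from baseline and no confidence interval for quality of life, although the same men are scored at baseline and nine later visits

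*Combined protocol and SAP*

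**What the plan says.** Secondary objective 1 in section 2.2 is to "Assess the incidence of grade 3 or greater late GU and GI toxicity and self-reported quality of life data". Section 6.1 schedules the instruments: "Symptom assessment (IPSS, SHIM, modified EPIC sheet, as per Appendix I) – At baseline, 3 and 6 months after treatment", then every 6 months to 3 years and yearly to year 5. The study calendar in section 7.0 agrees and lists them as quality of life measures. That is one baseline and nine follow-up assessments (3, 6, 12, 18, 24, 30 and 36 months, years 4 and 5), ten per man.

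The whole analysis is one sentence in section 8.2.1: "Patient reported quality of life will be summarized using means and standard deviation" for continuous measures, with contingency tables for categorical ones. It does not say how the summaries are arranged. Nothing elsewhere in the document names change from baseline, an interval for quality of life, a repeated-measures method, a key time point or a rule for missing questionnaires.

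The neighbouring analyses are specified more fully. Late toxicity (8.2.1) and control rates (8.2.2) are given 95% confidence intervals, and the cytokine work (8.2.4) is framed in terms of change.

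**The concern.** The trial has one arm, so a man's own baseline is the only internal reference for patient-reported urinary, sexual and bowel function. The other half of objective 1 counts only late toxicity of grade 3 or more. The SBRT studies cited in section 1.0 report such events as uncommon: 2 of 32 patients for rectal toxicity in one, and at most 2% GI and 4% GU in the other. Less severe harm would therefore show mainly in the questionnaires.

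A table of visit means and SDs lets a reader subtract one mean from another but not attach a valid standard error, because the correlation between a man's two scores is not reported. Each later mean also covers only the men who returned, and section 14.0 allows withdrawal for intercurrent illness or noncompliance, so loss may be related to health. At stake is the interpretation of one secondary objective.

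**Working it through.** **The plan's own figures.** Section 8.3 gives no precision figure for quality of life. Its figures concern the primary endpoint: "If 100 patients will finish 5 year follow up, the width of 95% confidence interval of BFFR will be less than 0.14", with 110 men in total.
- Width at 85%: 2 × 1.96 × √(0.85 × 0.15 / 100) = 0.13997. This reproduces.
- Sample size: 100 × 1.10 = 110, and 100 / 0.90 = 111.1. Close to the stated 110.

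From these I take n = 100 men at year 5, N = 110 at baseline and up to 10% lost.

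**Precision of change.** Assumptions, not in the document: equal SDs at the two visits and within-man correlation r of 0.3 to 0.7. Half-widths of the 95% interval for mean change, in SD units:
- two means treated as independent: 1.96 × √(2/n) = 1.96 × √0.02 = 0.277
- within-man change: 1.96 × √(2(1 − r)/n)
- model with baseline as an outcome, using all 110 baselines: 1.96 × √((1 − r²)/100 + (1 − r)²/110)

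| r | Independent | Within-man | Model | Independent / within-man |
|---|---|---|---|---|
| 0.3 | 0.277 | 0.232 | 0.228 | 1.20 |
| 0.5 | 0.277 | 0.196 | 0.194 | 1.41 |
| 0.7 | 0.277 | 0.152 | 0.151 | 1.83 |

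**Who is measured.** If a share d is lost and those men differ from the men retained by g SD, the observed mean is off by d × g. With g = 0.5 (assumed):
- d = 0.10 (the plan's limit): 0.10 × 0.5 = 0.05 SD
- d = 0.30 (illustrative): 0.30 × 0.5 = 0.15 SD

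The standard error of within-man change at n = 100 is √(2(1 − r)/100): 0.118, 0.100 and 0.077 SD for r = 0.3, 0.5 and 0.7. A shift of 0.05 SD is thus about half a standard error (0.42 to 0.65).

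A simulation in which loss depends on the baseline score only (N = 110, r = 0.5, baseline gap 0.5 SD, no true change, 5,000 runs) gave these biases in the estimated change, in SD units:

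| Loss | Difference of visit means | Change in men who returned | Likelihood model with all baselines |
|---|---|---|---|
| 10% | −0.025 | +0.025 | 0.000 |
| 30% | −0.076 | +0.073 | −0.001 |

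Restricting to paired change in those who returned does not remove the bias; it reverses the sign. Using every baseline in a likelihood model removes it under this mechanism.

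**Choice of model.** If baseline is instead a covariate and the result is read at the observed mean baseline, the usual standard error is √((1 − r²)/n). Relative to the within-man standard error this is √((1 + r)/2): 0.87 at r = 0.5 and 0.92 at r = 0.7. It treats the baseline mean as known and so understates uncertainty about population mean change. Placing baseline among the outcome time points avoids this.

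**The case against.** The strongest reply is that section 8.2.1 is brief rather than wrong. A change score is itself a continuous measure, so a mean and SD of change would fit the sentence. The objective is only to assess, with no hypothesis, margin or time point, and descriptive summary is a legitimate choice for it. This stands in part: the text does not exclude change scores. But it does not plan them, and an interval is missing however the sentence is read.

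Two stronger readings are tempting.
- A reader might infer that the trial cannot estimate change. Sections 6.1 and 7.0 contradict that: paired scores are collected, and the gap is only in the written analysis.
- A reader might convert the wider interval into a loss worth 1/(1 − r) times the patients, that is 2 to 3.3 times at r = 0.5 to 0.7. That follows only if repeated scores on the same men are analysed as independent samples, which the document nowhere proposes. With complete data the difference of visit means equals the mean within-man change, so the estimate itself loses nothing; its precision simply goes unreported.

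On attrition, the plan's dropout limit keeps the effect small. The document gives no questionnaire-completion rate, which may be lower than study retention, but it supplies no figure to show that. If the gap lies in scores never observed, a missing-at-random model does not repair it.

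**Conclusion.** The point holds as a gap in specification that is cheap to close. As written, the plan gives neither change from baseline nor any interval for quality of life. A reader left with visit means and SDs who treated them as independent would get an interval for change 1.2 to 1.8 times too wide; this rests on an assumed correlation of 0.3 to 0.7 and equal SDs.

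Mixing of real change with change in who is measured is a lesser matter: at most about 0.05 SD at the planned dropout with an assumed 0.5 SD gap, and 0.08 to 0.15 SD only at an illustrative 30% loss. The document does not support reading this as serious attrition bias. The primary endpoint, the sample size and the safety stopping rule are unaffected.

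**What to change.** In section 8.2.1, add for each score treated as continuous:
- Mean within-man change from baseline at each visit with 95% CI, from a repeated-measures model with baseline as one of the outcome time points, visit as a categorical factor and unstructured covariance.
- A named simpler covariance structure as fallback if the model does not converge. Ten time points need 10 × 11 / 2 = 55 covariance parameters from about 110 men.
- Questionnaire completion by visit.

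Keep the means, SDs and contingency tables as description.

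The cost is a few lines of text and minor programming, with no new data or visits. There are two limits to state. The model assumes data missing at random, which does not cover loss that depends on unobserved scores. And because section 3.2 excludes men with IPSS above 15, baseline IPSS is truncated, so mean IPSS change must be read with regression to the mean in mind.

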6.2 Follow-up Schedule

6.2.1 Patients will be assessed at three months and at six months after treatment, then every 6 months until 3 years, then annually until year 5. The patient will be off study after 5 years.

6.2.2 Patients who develop a rise in PSA of greater than 25% and of at least 0.3 ng/ml compared to the prior PSA will have PSA drawn every 3 months until PSA either returns to nadir value or rises to a value 2 ng/ml or more above the nadir. The nadir PSA is defined as the lowest PSA value after initiation of treatment. Time of failure will be the date of the first PSA that is 2 ng/ml or more above the nadir.

6.2.3 At any point in time, patients may undergo biopsy for histopathologic assessment of disease response, if there is evidence of recurrence.

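### The TLP rule in section 8.2.2 censors un-biopsied men at suspected failure, so local control is overstated unless almost none of them failed locally

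*Combined protocol and SAP*

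**What the plan says.** Under 8.2.2, TLP runs from enrollment to documented local progression and is estimated by Kaplan-Meier. Men with a new palpable abnormality or PSA failure "will also be offered biopsy to distinguish between local and distant failures". Section 6.2.3 is equally permissive: "patients may undergo biopsy for histopathologic assessment of disease response, if there is evidence of recurrence". For men who decline, 8.2.2 states: "Patients who do not undergo biopsy will be censored at the last point of time they were considered locally controlled", as judged by rectal examination and PSA, after which they count as not evaluable. Read in place, the sentence concerns men in whom failure is suspected. No sensitivity analysis and no report of biopsy uptake is planned.

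TDF is "measured from the date of enrollment to the date of documented metastatic disease". The next sentence adds: "Patients who have negative biopsy following PSA failure or palpable abnormality will be considered to have only distant failure". No event date is attached to that classification. Section 6.1 lists "Bone Scan - at baseline" and "Pelvic CT or other lymph node assessment - at baseline", with no later scheduled imaging.

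**The concern.** Kaplan-Meier treats a censored man as having the same later risk as those still under observation. Here men are removed because a sign of failure appeared, and the removal is dated before that sign. Any true local failure among them is lost as an event, while their earlier controlled time still counts. The TLP curve then depends partly on how many men accept biopsy. At the extreme, with no biopsies and no other documented local progression, it would read 100% local control whatever had happened.

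The TDF text raises a smaller, separate question. A negative prostate biopsy does not document metastasis, so two analysts could draw different TDF curves from the two adjacent sentences.

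At stake are two of the estimates that serve secondary objective 2 (clinical and pathologic control rates), which are to be reported with 95% confidence intervals. Those intervals reflect sampling error only, not this bias.

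**Working it through.** **Plan's own figure.** The documents state no TLP or TDF figure. Section 8.3 expects a 5-year BFFR of at least 85% and a 95% interval narrower than 0.14 with 100 completers. Check: 2 × 1.96 × √(0.85 × 0.15/100) = 0.13997, which agrees. This supplies N = 100 and at most F = 15 expected PSA failures.

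**Inputs from the documents.** Visits at 3, 6, 12, 18, 24, 30, 36, 48 and 60 months; the censoring rule above.

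**Assumed, not in the documents.** Biopsy uptake u and local share p, each 25-75%; a fully sensitive biopsy; biopsy-negative men stay at risk; failures spread over visits in proportion to interval length; no other dropout; PSA failures only. For the size (not the break-even), un-biopsied men have the same local share p.

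**Formulas.** At visit k there are F_k = F × (interval/60) failures.
- Un-biopsied men, F_k(1−u), leave before the visit, giving n_k at risk.
- Events are d_k = F_k·u·p, and planned S = Π(1 − d_k/n_k).
- Full-information local control = 1 − Fp/N.
- Worst case (every un-biopsied failure local) = 1 − F[up + (1−u)]/N.
- Break-even share among un-biopsied men = [N(1−S) − Fup]/[F(1−u)].

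**Central case, F = 15, u = p = 50%.**
- F_k is 0.75 at 3 and 6 months, 1.5 at each of the next five visits, and 3 at 48 and 60 months.
- First factor: 1 − 0.1875/99.625. Last factor: 1 − 0.75/89.5. Product: S = 96.08%.
- Full information: 1 − 7.5/100 = 92.5%. Overstatement: 3.58 points.
- Break-even: (3.921 − 3.75)/7.5 = 2.3%, or 0.17 of a man among 7.5.
- Worst case: 1 − 15 × 0.75/100 = 88.75%.

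**Grid, F = 15 (%, overstatement in points).**

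| u | p | planned | full information | overstatement | worst case | break-even |
|---|---|---|---|---|---|---|
| 25 | 25 | 99.00 | 96.25 | 2.75 | 87.81 | 0.6 |
| 25 | 50 | 97.99 | 92.50 | 5.49 | 86.88 | 1.2 |
| 25 | 75 | 96.99 | 88.75 | 8.24 | 85.94 | 1.8 |
| 50 | 25 | 98.04 | 96.25 | 1.79 | 90.63 | 1.1 |
| 50 | 50 | 96.08 | 92.50 | 3.58 | 88.75 | 2.3 |
| 50 | 75 | 94.12 | 88.75 | 5.37 | 86.88 | 3.5 |
| 75 | 25 | 97.13 | 96.25 | 0.88 | 93.44 | 1.7 |
| 75 | 50 | 94.25 | 92.50 | 1.75 | 90.63 | 3.4 |
| 75 | 75 | 91.37 | 88.75 | 2.62 | 87.81 | 5.1 |

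With F = 5, the overstatement is 0.3 to 2.8 points and the break-even 0.2% to 1.6%. At u = 100% there is no overstatement for either F. The largest break-even count with F = 15 is about 0.26 of a man (3.45% of 7.5), so one true local failure among the un-biopsied men is enough to push the curve too high.

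**TDF.** Men with PSA failure and a negative biopsy number F·u·(1−p). With F = 15 this runs from 15 × 0.25 × 0.25 = 0.9 to 15 × 0.75 × 0.75 = 8.4 per 100. Negative biopsies for a palpable abnormality without PSA failure are left out, so this is not an upper limit.

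**The case against.** **Reach.** TLP and TDF are descriptive secondary estimates. The primary BFFR rests on PSA alone, DFS counts PSA progression without biopsy, and no test, stopping rule or sample size uses TLP or TDF. This stands. A reader might infer that the main result is compromised; the documents do not support that.

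**Context already planned.** The plan says openly that un-biopsied men become not evaluable, and BFFR counts every PSA failure, so TLP will not be read alone. This stands in part. BFFR does not isolate local failure, and neither BFFR nor DFS captures an un-biopsied palpable abnormality without PSA failure.

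**Size.** The 8.2-point figure needs the maximum expected failures, low uptake and a high local share together. With 15 failures, the overstatement is below an approximate 95% half-width (n = 100) in 5 of the 9 cells, including the central one: 3.58 against 1.96 × √(0.9608 × 0.0392/100) = 3.80. With 5 failures it is below in 7 of 9. Men already shown to have metastases may also be the ones not biopsied, which would shrink the bias. All of this limits what can be said about size. The direction survives because the break-even is so low.

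**Back-dating.** A reader might add that follow-up rectal examination is discretionary, so censoring could be dated much earlier. Moving it all the way to baseline changes the planned figure by at most 0.2 points. The lost event drives the bias, not its date.

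**TDF wording.** A reader might infer that the plan definitely counts negative biopsies as distant events. The sentence sits in the TDF paragraph, so that reading is natural. Reading it as a label for the site of failure is also tenable, because the stated endpoint is documented metastasis. The documents do not settle it.

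**Conclusion.** The concern holds for direction. As written, the TLP rule overstates local control unless almost none of the un-biopsied men failed locally: above about 0.6% to 5.1% of them with 15 PSA failures per 100, the curve is too high. If none of them failed locally, or if all suspected men are biopsied, there is no overstatement.

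The size cannot be fixed from the documents. Under the stated assumptions it is about 0.9 to 8.2 points with 15 failures and 0.3 to 2.8 with 5. The upper figures are illustrations, not predictions.

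The TDF point is secondary: two adjacent sentences need reconciling, and the readings differ by about 1 to 8 men per 100 at 25-75% uptake with 15 PSA failures. Confidence is high on direction and on the TDF ambiguity, but not on magnitude.

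**What to change.** - Keep the planned TLP estimate and report biopsy uptake among men with PSA failure or a palpable abnormality.
- Add one worst-case TLP analysis that counts every un-biopsied suspected failure as a local event. Date it by the PSA-failure rule in 6.2.2 ("Time of failure will be the date of the first PSA that is 2 ng/ml or more above the nadir") or by the abnormal examination.
- If wanted, show a further sensitivity analysis that censors un-biopsied men with documented metastasis and no local sign. It should not be called a bound, because such men may also have failed locally.
- In the TDF paragraph, state whether a negative biopsy without documented metastasis is a TDF event and, if so, on what date.

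The cost is some rewording of 8.2.2 and one extra analysis, with no added biopsies or scans. PSA-failure dates come from scheduled tests, but abnormal-examination dates exist only where the discretionary examination was done. The downside is a wider and less favourable local-control range: with 15 failures, planned minus worst case is about 3.6 points (91.37 − 87.81, 75% uptake) to 11.2 points (99.00 − 87.81, 25% uptake).

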¹¹Patients who develop a rise in PSA of greater than 25% and of at least 0.3 ng/ml compared to prior PSA will have PSA drawn every 3 months until PSA either returns to nadir value or rises to a value 2 ng/ml or more above the nadir. The nadir PSA is defined as the lowest PSA value after initiation of treatment. Time of failure will be the date of the first PSA that is 2 ng/ml or more above the nadir.

¹²At any point in time, patients may undergo biopsy for histopathologic assessment of disease response, if there is evidence of recurrence.

¹³Androgen deprivation therapy will be given for 4 months total, (must be given \geq 1 month prior to the start of radiation therapy)

¹⁴Radiation will be given in 5 fractions over 2 weeks (treatment to be performed every other day)

¹⁵Rectal exam is required at baseline. During follow-up it is at the discretion of the treating physician

PI: [name]

IRB00079078

December 20, 2021

¹⁶ Follow-up appointments for 1 month, 2 months, and 3 months have a +/- 7 day tolerance window and all other follow-up appointments have a +/- 30 day tolerance window.

¹⁷ CT simulation will occur prior to radiation therapy and then again during radiation therapy as a QA procedure after fraction 3 only if patients had fiducial placement.

*CT/MRI and bone scan optional except for the patients who are:

1. Gleason 4+3
2. >50% cores positive
3. >1 intermediate risk factor (GS 7, PSA ≥ 10 and T2b-T2c).

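### Section 8.2.2 makes documented metastasis the distant-failure event, then assigns distant failure after a negative biopsy with no metastasis documented and no event date

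*Combined protocol and SAP*

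**What the plan says.** Section 8.2.2 covers clinical and pathologic control, a named secondary objective (section 2.2), using Kaplan-Meier curves with 95% confidence intervals. Four of its statements matter here.

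- **Biopsy trigger (Time to Local Progression paragraph).** "Patients with new palpable abnormality on digital rectal examination or PSA failure at any point in time will also be offered biopsy". Either finding alone is enough. The stated purpose is to separate local from distant failure.
- **TDF event.** "Time to Distant Failure (TDF) will be measured from the date of enrollment to the date of documented metastatic disease".
- **Negative-biopsy rule, the very next sentence.** "Patients who have negative biopsy following PSA failure or palpable abnormality will be considered to have only distant failure".
- **DFS progression.** "Progression will be documented by PSA, bone scan, or biopsies". A palpable finding is not on that list.

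Other sections give the context. Section 6.2.2 dates PSA failure: "Time of failure will be the date of the first PSA that is 2 ng/ml or more above the nadir". Section 6.1 lists "Bone Scan - at baseline", and there it is optional for some men; the study calendar (section 7.0) schedules no bone scan or pelvic imaging in follow-up. The calendar marks a digital rectal exam at each follow-up visit from 3 months to year 5, but its footnote adds: "During follow-up it is at the discretion of the treating physician".

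**The concern.** The negative-biopsy rule infers distant failure by exclusion: the man has failed, the prostate biopsy is clear, so the failure lies elsewhere. That reasoning needs independent evidence that a failure exists. PSA failure supplies it. A palpable abnormality does not, because it is itself the suspected local failure. Once the biopsy is negative and the PSA is controlled, no recorded failure remains to be given a site.

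The rule nevertheless treats the two triggers alike, and in both it sets aside the requirement in the sentence before it. Two analysts with the same data could then report different TDF curves, one counting only documented metastases and the other adding every biopsy-negative man at a date of the analyst's choosing. Distant failures may be few in this trial, so a handful of added events could change the reported rate noticeably.

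**Working it through.** The documents give no figure for distant failure, so there is none to reproduce. The check sets the rules side by side and then sizes one misclassified man.

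**Step 1. Apply each rule to each type of patient.** All are taken to be alive, with no positive bone scan unless stated.

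| Patient | TDF event sentence | Negative-biopsy sentence | DFS | BFFR (primary) |
|---|---|---|---|---|
| A. Palpable abnormality, negative biopsy, no PSA failure | No event | Distant failure | No event | Failure-free |
| B. PSA failure, negative biopsy, no metastasis documented | No event | Distant failure | Event (PSA) | Failed |
| C. Metastasis shown on bone scan | Event | Not needed | Event | Depends on PSA |

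Patients A and B get opposite answers from two adjacent sentences. Patient A is the clearer error: a distant failure should also be a DFS event, and he is not one.

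**Step 2. Look for a date.** For patient B, section 6.2.2 dates the PSA failure, but nothing says that this is the TDF date. For patient A, the date could be that of the examination or of the biopsy; the plan names neither.

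**Step 3. Look for a limit elsewhere.** No section restricts the rule to men with PSA failure. None makes the label depend on imaging, and no imaging is scheduled after baseline that could confirm or remove it.

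**Step 4. Size per man.** Inputs from section 8.3: 110 men planned, 100 expected to complete 5 years.

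- 1/110 = 0.9 percentage points
- 1/100 = 1.0 percentage point

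This is a crude proportion.

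**Step 5. Illustration with assumed counts.** The documents give neither the number of true distant failures (m) nor the number of men like patient A (k). The crude proportion is (m + k)/110:

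| m | k = 0 | k = 1 | k = 3 | k = 5 |
|---|---|---|---|---|
| 3 | 2.7% | 3.6% | 5.5% | 7.3% |
| 5 | 4.5% | 5.5% | 7.3% | 9.1% |

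**Step 6. Ceiling for patient B.** Section 8.3 expects a 5-year BFFR of at least 85%. Among 100 completers that is at most 100 × (1 − 0.85) = 15 men with PSA failure. Only those who accept biopsy, have a negative result and have no documented metastasis are affected; that share is not given.

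**Step 7. Primary endpoint.** BFFR uses PSA alone. Its stated interval width (under 0.14) reproduces as 2 × 1.96 × √(0.85 × 0.15/100) = 0.13997 and does not involve this rule.

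**The case against.** The strongest reply is that the rule only assigns a site among men already judged to have failed. Section 8.2.2 offers biopsy in order to tell local from distant failure, section 6.2.3 allows it when there is evidence of recurrence, and DFS does not accept a palpable finding as progression. On that reading patient A never comes under the rule. The reading is plausible, but the text does not secure it: both the biopsy trigger and the negative-biopsy sentence name a palpable abnormality as an alternative to PSA failure. It also leaves patient B's conflict untouched.

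Other points on that side stand and limit the claim:

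- A reader might infer that men with no evidence of cancer will be counted as metastatic. The documents do not support this. The man does have a palpable finding, they do not address false-negative biopsies, and the TDF sentence still requires documented metastasis. What is established is a conflict, with a label that follows from one of the two sentences.
- A reader might infer a definite downward bias in distant control. That depends on which sentence the analyst follows and on how many such men occur. Follow-up rectal examination is discretionary and biopsy is only offered, so the number may be small.
- Disagreement with BFFR is not an error in itself, since a PSA endpoint and a clinical endpoint may differ in one man. The real inconsistency is with the TDF definition and with DFS.
- No hypothesis test, stopping rule or sample-size calculation uses TDF.

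**Conclusion.** The point holds as a contradiction within section 8.2.2. If followed, the negative-biopsy sentence gives a wrong classification for a man with a palpable abnormality, a negative biopsy and no PSA failure. For a man with PSA failure and a negative biopsy it gives an undocumented one. Neither has a defined event date.

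The size is about 0.9 to 1.0 percentage point of distant failure for each man counted this way, assuming 100 to 110 men in the denominator. The total cannot be estimated from the documents and may be zero for the palpable-abnormality group. The effect is confined to a descriptive secondary endpoint and its consistency with DFS. It is worth correcting because the rule is wrong as written and cheap to change.

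**What to change.** Replace the negative-biopsy sentence in section 8.2.2 with three rules:

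1. A TDF event is counted only when metastatic disease is documented, at the date of that documentation.
2. A palpable abnormality with a negative biopsy and no PSA failure is not a failure; the man remains at risk for all endpoints.
3. PSA failure with a negative biopsy and no documented metastasis is reported as a separate biochemical-only or site-unknown category. A sensitivity analysis counts these men as distant failures at the PSA failure date defined in section 6.2.2.

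Deleting only the reference to a palpable abnormality would not be enough, because the men with PSA failure would still be called distant failures against the TDF definition.

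The cost is a few sentences, one extra category and one sensitivity analysis, with no new procedure. The downside is that the main TDF analysis may have fewer events.
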